6.4 Safety Laboratory Parameters

Laboratory parameter results and changes from baseline will be summarized by visit. Summaries will be limited to values assessed at the Central Laboratory. Laboratory values collected at local laboratories will be provided in listings, but not summarized. Shift tables from baseline to subsequent study visits will also be generated based on the Central Laboratory measurements for ALT, AST, total bilirubin, serum creatinine, urine protein:creatinine ratio, creatine phosphokinase, sodium, hematocrit, platelets, white blood count, neutrophils, and lymphocytes. Counts and percentages of laboratory values outside the normal reference range will be summarized by laboratory parameter, treatment group and visit. The denominator for percentages will be the number of subjects in the particular treatment group with measurement at a specified visit. Laboratory values outside the reference ranges will be flagged in the listings. Summaries will be presented separately for the double-blind and avacopan treatment periods, respectively.

The subject incidence of elevated laboratory values of ALT, AST, total bilirubin, alkaline phosphatase, creatinine, potassium, and creatine phosphokinase (CPK) as assessed by the Central Laboratory, will be summarized by treatment group and Grade, as defined per Common Terminology Criteria for Adverse Events (CTCAE) Version 5. Shift from baseline to highest CTCAE grade during the study period will also be produced for these laboratory parameters based on the Central Laboratory measurements. The same summary by treatment and CTCAE grade will be produced for subject incidence of low neutrophils, low lymphocytes, low leukocytes, low hemoglobin, and low platelets. Shift from baseline to highest CTCAE grade during the study period will also be produced for these laboratory parameters. A by-subject listing including all data for these laboratory parameters including CTCAE grade for subjects with any abnormality will be provided.

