4.4. Removal of Patients from Therapy

Investigators must clearly distinguish between discontinuation of study drug treatment (avacopan or placebo) and withdrawal from the study. Patients who discontinue study drug treatment or who initiate medication changes (including those prohibited by the protocol that comprise treatment failure) will not be automatically withdrawn from the study, but all efforts must be made to continue to follow the patients for all regularly scheduled visits.

Investigators must take appropriate measures to make sure that patients are motivated to comply with all requirements of the protocol in order to minimize the amount of missing data. Patients who discontinue study treatment early or initiate medication changes (including those prohibited by the protocol) should continue to be followed for all regularly scheduled visits for safety and efficacy assessments. Investigators and their staff must take measures to actively maintain contact with their patients in the study, such as telephone calls, texts, or emails between visits, and offers for transportation support to visit the study site.

Patients may be withdrawn from the study for only one of the following two reasons:

1. Patient withdrawal of consent to contribute additional outcome information;
2. Loss to follow-up.

Patients may discontinue study drug treatment for any of the following reasons:

1. Patient withdrawal of consent;
2. The Investigator may discontinue study drug treatment if, in his/her clinical judgment, it is in the best interest of the patient;
3. The Sponsor may request discontinuation of study drug treatment for safety reasons. If a patient develops any of the following lab abnormalities:

If a patient develops ALT or AST $>3x$ ULN, additional testing should be performed immediately and repeated in one week to assay for total and fractionated serum bilirubin concentration, serum albumin concentration, and prothrombin time or INR, in addition to repeat transaminase (ALT, AST) testing. In addition, if a patient develops Grade 3 or greater increased hepatic transaminases (>5 times the upper limit of normal), or if a patient develops Grade 2 or greater increased transaminases (>3 times the upper limit of normal) with elevation of bilirubin to >2 times the upper limit of normal, dosing with study drug must be paused in this patient.

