3.1.8 Adjustments for Potential Impact of COVID-19

COVID-19 pandemic may impact the conduct of the study from different aspects including quarantines, site closures, travel limitations, interruptions to the supply chain for the investigational product, or other considerations if site personnel or trial subjects become infected with COVID-19.

Data fields to capture visit impact due to COVID-19 were added to the database including visit status (visit not completed/in-person visit partially completed/performed virtually), if visit status was due to COVID-19, whether the visit was completed outside of window due to COVID-19 and how or why participation was impacted by COVID-19 (travel restrictions, study site closed, patient chose not to attend site visit, renal biopsy not allowed at site requiring an extended randomized treatment period, patient received COVID-19 diagnosis, lack of study site personnel, lack of home nursing, local labs used instead of protocol-defined central labs and other). The data will be included in listings. Additionally, if a subject discontinued study treatment early or discontinued early from the study due to COVID-19, these data will be summarized as part of subject disposition. Local laboratory data collected due to COVID-19 will be listed.

Adjustments for missing data due to COVID-19 are incorporated into the multiple imputation analyses, completer analyses, per-protocol analyses and sensitivity analyses. Additionally, wider analysis windows are being allowed in order to capture critical data (e.g. renal biopsy data at Week 26 and Week 52) to reduce missing data. See Section 3.1.2 and Section 5 for additional details.

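### SAP 6.4 builds its worst-grade laboratory tables from central-laboratory values only, so an abnormality measured only at a local laboratory would be left out of them

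*SAP*

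**What the plan says.** SAP 6.4 opens with a general rule: "Summaries will be limited to values assessed at the Central Laboratory". The next sentence adds the consequence: "Laboratory values collected at local laboratories will be provided in listings, but not summarized".

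The rule is repeated for the graded chemistry tables. Incidence of raised ALT, AST, total bilirubin, alkaline phosphatase, creatinine, potassium and CPK, "as assessed by the Central Laboratory, will be summarized by treatment group and Grade". Likewise, "Shift from baseline to highest CTCAE grade during the study period will also be produced for these laboratory parameters based on the Central Laboratory measurements".

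For blood counts the wording is indirect: "The same summary by treatment and CTCAE grade will be produced for subject incidence of low neutrophils, low lymphocytes, low leukocytes", with haemoglobin and platelets following. The central laboratory is not named again there, so the restriction comes from the general rule and from the reference to the same summary.

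SAP 3.1.8 lists, among the recorded ways in which COVID-19 could affect a visit, "local labs used instead of protocol-defined central labs", and says that such local results will be listed. SAP 3.1.4 rules out imputation of missing safety laboratory values.

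**The concern.** A by-visit mean or by-visit shift gains from one assay and one set of ranges, so central-only is a sound choice there. A worst-grade table asks something else: did this subject, at any time after dosing, reach a given grade? It should use every value observed. If the only high ALT or low neutrophil count was measured locally and the subject's central values were normal, the table shows that subject without the event.

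The parameters affected are those the trial watches most closely. Protocol 4.4 sets rules for pausing or stopping study drug based on transaminases, white cells, neutrophils, lymphocytes and CPK. Protocol 1.2 describes transaminase elevations in a related study. Protocol 12.3.2 explains that haematology monitoring was made monthly after safety review by the data monitoring committee. The SAP is based on a CRF version of May 2020 and has a primary-analysis cutoff of 1 October 2020, so part of the follow-up fell within the pandemic.

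**Working it through.** The plan states no figure on this point, so there is none to reproduce. The check is a reading of the sections together, followed by a simple scale.

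**Path of a local-only value through the plan**

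| Output | Local value included? | Source |
|---|---|---|
| By-visit means, shifts, out-of-range counts | No | SAP 6.4 |
| Chemistry incidence by CTCAE grade | No, explicit | SAP 6.4 |
| Chemistry shift to highest grade | No, explicit | SAP 6.4 |
| Blood-count incidence and highest-grade shift | No, by the general rule | SAP 6.4 |
| Laboratory listings | Yes | SAP 6.4, 3.1.8 |
| Abnormalities that prompt pausing or stopping | Optional; source not stated | SAP 2.3.7.2 |
| Adverse event tables | Only if reported as an AE | SAP 6.3, Protocol 7.2.4 |

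SAP 3.1.4 closes the remaining route: a central value replaced by a local one stays missing in the laboratory tables.

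**Direction.** Let C be a subject's central grades after dosing and L the local ones. The plan reports max(C). The worst grade observed is max(C and L together), and max(C) can never exceed it. For subject incidence, leaving out L can therefore only lower the count or leave it unchanged.

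**Can local values be graded?** The thresholds that Protocol 4.4 labels by grade are multiples of the upper limit of normal (transaminases above 3 and 5 times, CPK above 5 times) or absolute counts (for example, white cells below 2 × 10⁹/L). The first kind needs the value and that laboratory's own limit. The second needs only the value in common units.

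**Scale.** The planned size is about 22 per arm in each C5b-9 stratum (SAP 2.2.2), hence 2 × 22 = 44 per arm in both strata combined. One subject missing from the numerator changes incidence by:

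- 1/22 = 0.045, about 4.5 percentage points, in one stratum;
- 1/44 = 0.023, about 2.3 percentage points, in both strata at planned size.

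SAP 10 says that the non-elevated stratum is small. If the elevated stratum reached its planned size, the combined figure would lie between these two.

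**Frequency.** If a share f of visits were measured only locally, independently of one another, an abnormality present at k visits would escape every central sample with probability f^k. The documents give no value for f, so no expected undercount can be calculated.

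**Denominator.** SAP 6.4 defines one for the by-visit out-of-range table (subjects measured at that visit), but none for the CTCAE subject-incidence table.

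**The case against.** The case for leaving the rule alone has real substance.

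- **Other tables exist.** A reader might infer that local results are shut out of every safety summary. They are not. SAP 6.3 tabulates adverse events with no restriction by laboratory and names hepatic enzyme elevations, white cell decreases and CPK elevations as events of interest. Protocol 7.2.4 counts abnormal laboratory findings as possible adverse events. This stands, but as a partial safeguard. It depends on the investigator reporting the value. Severity is defined by limitation of usual activities (SAP 6.3), and Protocol 7.2.4.1 makes CTCAE grading of laboratory values optional. A silent high-grade value may therefore not appear as one.
- **Nothing is hidden.** Local values are listed, and SAP 6.4 promises a by-subject listing with CTCAE grade for subjects with any abnormality. This also stands, but a listing does not give incidence by arm.
- **Local use may be rare.** One could read SAP 3.1.8 as saying that local laboratories took over from the central one. It gives local use as one recorded category among several, with no count.
- **Retesting is not shown to be local.** Protocol 4.4 says that after a transaminase rise "additional testing should be performed immediately and repeated in one week", and a reader might suppose that this happens locally. The section does not say where. Protocol 7.2.2 places the safety tests, including the coagulation tests tied to that retest, with the central laboratory. The point does not rest on retesting.
- **Persistent abnormalities would usually be caught.** Protocol 3.4 plans liver and haematology monitoring at least every 4 weeks, so a lasting change would probably reach a central sample. That is the f^k argument, and it holds. The exposure is to short-lived peaks.
- **The rule is even-handed.** It is pre-specified and applies to both arms, and unscheduled local testing brings uneven ascertainment. This is a good reason to keep the central-only table, but not to make it the only one.

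**Conclusion.** The point holds as a gap in the SAP 6.4 laboratory tables. As written, an abnormality measured only at a local laboratory does not enter the CTCAE incidence or highest-grade tables. This is explicit for chemistry and follows from the general rule for blood counts. Any effect on subject incidence is in one direction, towards fewer events. One missed subject is worth about 4.5 percentage points at 22 per arm and 2.3 at 44.

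The documents do not support anything stronger. They do not show that any event was missed, how many values were local, or that the comparison between arms is biased. The scale assumes planned enrolment and a single missed subject; it is an illustration, not an estimate. No efficacy conclusion is touched. The change is worth making because it is cheap and concerns the trial's main laboratory safety signals.

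**What to change.** In SAP 6.4:

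- Keep by-visit means and by-visit shifts on central values only.
- Produce subject incidence by CTCAE grade and shift to highest grade also from all post-dose central and local values, for chemistry and blood counts alike. At the least, add this as a supplementary table beside the central-only one.
- Grade local values against the reference range of the laboratory that produced them.
- State the denominator of the CTCAE subject-incidence table.
- Footnote, by arm, how many worst grades came from a local laboratory.

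The cost is a short SAP addition plus standardisation of units and ranges for local values already captured for the listings. The downside is some heterogeneity from unscheduled local testing; showing the two tables side by side makes its effect visible.

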6.5 Vital Signs

Vital sign results and changes from baseline will be listed and summarized by study visit and treatment group separately for the double-blind and open-label periods.

6.6 ECG Parameters

Abnormal ECG findings will be listed by treatment group and study visit, and clinical significance of abnormalities indicated.

6.7 Physical Examinations

Physical examination findings will be listed by treatment group and study visit, and clinical significance of abnormalities indicated.

6.8 Pharmacokinetic and Pharmacodynamic Marker Analysis

Individual plasma concentrations of avacopan and its significant metabolite CCX168-M1 will be listed, plotted, and summarized descriptively and graphically. When possible, the mean steady state trough concentrations and the terminal elimination half-life will be calculated. PK parameters such as C_{max}, T_{max}, and AUC_{0-6hr} will be calculated in adolescents for avacopan and metabolite CCX168-M1 based on plasma concentrations for samples collected on Day 1 and on Day 183. Plasma and urinary PD markers will be summarized and may be analyzed using methods analogous to the efficacy parameters. The relationship between PK parameters and renal function based on eGFR will also be evaluated. The data may also be used to evaluate the PK/PD relationship of avacopan treatment. To this end, the change and/or percent change from baseline in C3G Histologic Index for disease activity, C3G Histologic Index for disease chronicity, eGFR, UPCR, urinary MCP-1:creatinine ratio, or other biomarkers may be used as PD markers.

Details of the PK and PD analysis will be described in a separate analysis plan and will be reported in a separate report

7 DATA MONITORING COMMITTEE

In addition to continuous safety monitoring by the Medical Monitor and clinical staff, an external Data Monitoring Committee (DMC) has been established to monitor the safety of subjects over the course of the study. The DMC consists of external physicians and a biostatistician. A DMC charter was developed before start of the study and the DMC functions according to the charter. The DMC has regular meetings, once every 3 to 6 months, depending on study enrollment rate. Ad hoc meetings may be scheduled if unanticipated safety events occur. After review of data at each meeting, the DMC makes recommendations about further conduct of the study.

8 ANALYSIS TIMING

Per the protocol, the earliest time point at which the primary efficacy analysis can occur is when the last enrolled subject in the primary population (subjects in the elevated C5b-9 stratum) has completed the Week 26 visit. The second (follow-up) analysis will be performed when all subjects have completed the full study after Week 60. No Type I error adjustment will be made for the second analysis since the endpoints for the second analysis are different from the first analysis and it is considered to be supportive.

Additionally, enrollment for the stratum with C5b-9 levels \leq 244 ng/ml could terminate early, if subject enrollment in the elevated stratum (C5b-9 level >244 ng/mL) reaches target enrollment first. Further, both strata can be analyzed separately and independently. The stratum with elevated levels (primary population) will be analyzed first should the stratum with C5b-9 \leq 244ng/ml (secondary population) continue a blinded follow up.

8.1 Week 26 Primary Analysis

The Week 26 Primary Efficacy Analysis will be performed including all subjects who reach Week 26 or discontinued the study by 01-Oct-2020. The data beyond Week 26 will also be summarized for data collected and cleaned at the time of the data cutoff. As of 01-Oct-2020, there are four subjects (2 patients in each of the two C5b-9 stratum) who are ongoing and will not reach Week 26 at the time of data cutoff of the primary analysis. Details of subjects who had major protocol deviations that could affect the primary efficacy outcome will be documented in a memo along with other patient population decisions at the conclusion of blinded data review prior to the data freeze.

The final analysis will be performed when all subjects have completed the full study after Week 60. The final analysis will repeat the primary analysis on all subjects' data, including patients who are ongoing for the week 26 renal biopsies now and enrolled in the future. The final results will be consider as supportive of the primary analysis. All study results will be included in a single Clinical Study Report.

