3.2. Randomization

Patients will be randomized using an interactive response technology (IRT) system and a minimization algorithm, using the stratification factors, in a 1:1 ratio to one of two treatment groups:

Group A: avacopan-matching placebo twice daily

Group B: avacopan 30 mg twice daily

The earliest timepoint at which the primary efficacy analysis can occur is when the last enrolled patient in the primary population (patients in the elevated C5b-9 stratum, see [Section 8.2.1](#)) has completed the Week 26 visit. After the 26-week double-blind period, the avacopan group will continue receiving avacopan for another 26 weeks, and the avacopan-matching placebo group will be switched over in a blinded manner to receive 30 mg avacopan twice daily treatment, instead of avacopan-matching placebo, for another 26 weeks.

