8. STATISTICAL METHODS

Details of the statistical analysis will be provided in a separate statistical analysis plan (SAP), which will be written, finalized, and approved prior to database lock and will be included in the Clinical Study Report (CSR) for this protocol. The SAP will supersede the statistical analysis methods described in this clinical protocol. Any major deviations from the protocol will be documented and described in the final report. If changes to principal features stated in the protocol are required, these will be documented in a protocol amendment. The final SAP will take into account any amendment to the protocol. Data analysis and writing of a CSR for all study data will be performed by the designated CRO in accordance with its SOPs. Analysis of PK and PD data, and writing of PK and PD reports will be performed by designated PK and PD teams in accordance with their standard operating procedures.

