8.1. Patient Populations

8.1.1. Intent-to-Treat Population

For the purposes of data analysis, the ITT Population will include all patients who have provided written Informed Consent/Assent and are randomized in the study.

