8.7. Statistical Analysis Methodology

A statistical analysis plan (SAP).with specific details of all the planned analyses and sensitivity analyses will be generated and approved before unblinding the data for analysis.

All statistical testing will be two-sided, with the Type I error rate at $\alpha = 0.05$.

The efficacy analyses for the efficacy endpoints will be performed in the ITT and PP populations, with the ITT analysis being the primary analysis.

The earliest timepoint at which the primary analysis of the efficacy endpoints can be conducted is when all patients in the elevated stratum have completed at least the Week 26 study visit. Additionally, enrollment for the stratum with C5b-9 levels ≤ 244 ng/ml could terminate early, if patient enrollment in the other stratum (C5b-9 level > 244 ng/mL) reaches target enrollment first. Further, both strata can be analyzed separately and independently. The stratum with elevated levels (primary population) will be analyzed first should the stratum with C5b-9 ≤ 244 ng/ml (secondary population) continue a blinded follow up – further details will be provided in the SAP.

For efficacy analysis, to control for the Type I error rate, a gate-keeping procedure will be applied for the analysis of the primary efficacy endpoint (percent change in C3G Histologic Index for disease activity). The primary endpoint will be tested in the elevated C5b-9 stratum first with a two-sided $\alpha = 0.05$. If this test reaches statistical significance, then the primary endpoint will be tested in the non-elevated C5b-9 stratum with a two-sided $\alpha = 0.05$. If the test in the elevated stratum fails to reach statistical significance, then the test in the non-elevated C5b-9 stratum will not be performed and only performed as an exploratory analysis. The statistical analysis for the secondary endpoint (C3G Histologic Index for disease chronicity) will be tested at a 0.05 α -level only if the primary endpoint in the same stratum reaches statistical significance.

Another analysis will be performed when all patients have completed the study after week 60. Individual patient group assignment will remain blinded to investigators and patients until after the analysis of the data from the second analysis in order to maintain study integrity.

Baseline is defined as the last value prior to start of dosing with study medication (typically the Day 1 pre-dose value).

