1 INTRODUCTION

The purpose of this document is to provide a description of the statistical methods and procedures to be implemented for the analysis of data from ChemoCentryx, Inc. Protocol CL011_168. This document is based on protocol amendment 4.0 (20MAR2019) and CRF version 11.2 (07MAY2020). If circumstances arise during the study such that more appropriate analytic procedures become available, the statistical analysis plan (SAP) may be revised. The statistical definitions and analytical methods described in this SAP supersede that in the protocol. Any revisions to the primary endpoint analyses and significant revisions to the secondary endpoint analyses will be made prior to the database lock/snapshot. Reasons for such revisions will be described in the final Clinical Study Report (CSR).

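### The 01-Oct-2020 primary analysis breaks the SAP's own Week 26 timing rule and drops two elevated-stratum patients from its ITT set; Section 10 lists neither change, and the stated reason for no alpha adjustment is false

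*SAP*

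**What the plan says.** **Timing.** Protocol 3.2: "The earliest timepoint at which the primary efficacy analysis can occur is when the last enrolled patient in the primary population" (the elevated C5b-9 stratum) has completed Week 26. Protocol 8.7 puts it as "when all patients in the elevated stratum have completed at least the Week 26 study visit", and Protocol 8.9 agrees. SAP Section 8 presents the rule as current and as the protocol's: "the earliest time point at which the primary efficacy analysis can occur is when the last enrolled subject in the primary population" has completed that visit. SAP 8.1 then says: "The Week 26 Primary Efficacy Analysis will be performed including all subjects who reach Week 26 or discontinued the study by 01-Oct-2020". It adds that on that date "there are four subjects (2 patients in each of the two C5b-9 stratum) who are ongoing and will not reach Week 26".

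**Analysis set.** Protocol 8.1.1: "the ITT Population will include all patients who have provided written Informed Consent/Assent and are randomized in the study". SAP 3.2.2 keeps the name ITT but requires at least one dose and a baseline activity score above 0, and leaves out ongoing patients without a Week 26 visit. SAP 3.2.1 carries the protocol's wording over to a separate Randomized Population, but SAP 5.2.1 bases the primary analysis on ITT.

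**Record of changes.** SAP Section 10 lists three changes: the roles of the C5b-9 populations, the baseline-score-0 exclusion and the order of secondary endpoints. Protocol Section 8 lets the SAP supersede its methods, but also says: "If changes to principal features stated in the protocol are required, these will be documented in a protocol amendment". SAP Section 1 rests on amendment 4.0 of 20 March 2019.

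**Second analysis.** SAP Section 8 makes no alpha adjustment for two reasons: the endpoints differ from those of the first analysis, and the analysis is supportive. SAP 8.1 says the final analysis repeats the primary analysis on all patients, including those now ongoing or enrolled later, and again calls it supportive.

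**Combined test.** Randomisation is stratified by C5b-9 (SAP 2.2.2). The combined-strata test in SAP 5.2.2 reuses the ANCOVA of SAP 5.2, with treatment and baseline score only. SAP 3.2.5.3 calls the combined set the secondary population; SAP Section 8 still gives that name to the non-elevated stratum.

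**The concern.** Section 8 and Section 8.1 cannot both govern when the confirmatory analysis is done. As written, the analysis runs before its own condition is met, on a set called ITT that leaves out randomised patients of the primary population. The final analysis then repeats the same test on a larger set under the same name, so the study report could hold two ITT results for one hypothesis.

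A reader who checks Section 10 for departures from the protocol would find neither the early cut-off nor two of the three changes to ITT. A reader who checks why alpha is not adjusted would find a reason that the next subsection contradicts.

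The combined test is a different kind of point. Leaving out a factor that was used to stratify randomisation gives away precision for no benefit.

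**Working it through.** **1. Timing and set, side by side**

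| Item | Rule | What SAP 8.1 or 3.2.2 does | In SAP Section 10? |
|---|---|---|---|
| Start of primary analysis | Last enrolled elevated-stratum patient has completed Week 26 (Protocol 3.2, 8.7, 8.9; SAP 8) | 01-Oct-2020, two such patients ongoing | No |
| Ongoing patients | In ITT (Protocol 8.1.1) | Excluded | No |
| At least one dose | Not required | Required | No |
| Baseline score 0 | In ITT | Excluded | Yes |

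Three of the four departures are missing from the list.

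**2. Size of the timing departure**

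Inputs from SAP Section 9: difference 35 points, SD 34, two-sided 0.05, power 90%, 22 per group. Actual enrolment is not given, so the planned 44 is assumed.

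The plan's figure first. By normal approximation, n = 2(1.960 + 1.282)² × (34/35)² = 19.8, so 20 per group. The exact t calculation needs 21. The stated 22 is adequate.

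Now the loss of two patients (2/44 = 4.5%), with SE = 34 × √(1/n₁ + 1/n₂) and power from the noncentral t with noncentrality 35/SE:

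| Split | SE | 95% CI half-width | Power |
|---|---|---|---|
| 22 + 22 | 10.25 | 20.7 | 0.9155 |
| 21 + 21 | 10.49 | 21.2 | 0.9023 |
| 20 + 22 | 10.50 | 21.2 | 0.9016 |

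In 1,000,000 simulated trials per setting, with 21 per arm nested in 22, the significance decision differs between the two sets in 2% of trials under no effect, 7% at 20 points and 3% at 35 points.

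**3. Size of the repeat**

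Test statistics at 42 and 44 patients have correlation √(42/44) = 0.977. Under the null, the bivariate normal chance that at least one exceeds 1.96 in absolute value is 0.060. If only the first look counts, it is 0.050.

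**4. C5b-9 in the combined ANCOVA**

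Assumptions: 22 per arm elevated; m = 2 to 10 per arm non-elevated (the SAP says only that this stratum is small); baseline–outcome correlation 0.4; arms balanced within stratum. Let p = m/(22 + m), and let d be the difference in stratum means in SD units. Without the stratum term, the residual variance is 0.84 + p(1 − p)d²; with it, 0.84, where 0.84 = 1 − 0.4². The CI width ratio is r = √[0.84/(0.84 + p(1 − p)d²)]. Balance within strata means the treatment estimate itself carries no between-stratum variation, so the actual error without the term is about 2[1 − Φ(1.96/r)].

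| d | m | p(1 − p) | CI narrowing with term | Type I error without term |
|---|---|---|---|---|
| 0.5 | 2 | 0.076 | 1.1% | 0.048 |
| 0.5 | 10 | 0.215 | 3.1% | 0.043 |
| 1 | 2 | 0.076 | 4.3% | 0.041 |
| 1 | 10 | 0.215 | 10.8% | 0.028 |

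Simulation (60,000 trials per setting) agrees: 0.044–0.048 and 0.027–0.041 without the term, 0.048–0.051 with it. If d = 0, the cost is one degree of freedom. With 48 patients the t quantile moves from 2.0141 to 2.0154, or 0.06%.

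**The case against.** The strongest defence is that nothing was hidden. SAP 8.1 gives the date, the number of patients and their strata, SAP 3.2.2 states the exclusion, and the same patients enter the final analysis. A calendar date does not select on outcome. The SAP may supersede protocol methods, and Section 10 is not the only place for a record: Protocol Section 8 sends major deviations to the final report, SAP Section 1 sends reasons for revisions to the study report, and SAP 8.1 promises a memo on population decisions before the data freeze. Whether this cut-off is a principal feature that needs an amendment is not defined.

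Most of this stands, and it limits the point to rule, label and record. It does not remove it. Section 8 does not supersede the timing rule; it repeats it as the protocol's, and the next subsection departs from it. A later memo does not correct that sentence, or a Section 10 that gives one of three changes to ITT.

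The defence is also right that the repeat is called supportive twice, so only the first of the two reasons fails. On C5b-9, adding the factor to the by-arm imputation models and to the van Elteren strata was not shown to help. The cells may be sparse, and the SAP already foresees dropping factors. Only the ANCOVA term is pressed.

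A reader might also see uncontrolled error in the chronicity test. Read literally, SAP 3.1 ties that test to the same stratum, which the combined set is not. On that reading there is no inflation (0.041–0.046 in simulation).

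**Conclusion.** Two texts are wrong as written. SAP Sections 8 and 8.1 conflict on when the primary analysis may start, with a set misnamed ITT and three departures missing from Section 10. The different-endpoints reason in Section 8 is contradicted by Section 8.1. Both should be corrected. One model term is a nearly free improvement.

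The numerical stakes are small. The power loss is about 1.3 points if the elevated stratum reached 44, which the documents do not confirm.

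A reader might infer three stronger things, none of which the documents support:

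- **The early cut-off biases the primary result.** Exclusion depends on calendar date, so no bias is expected if the date was set blind to outcomes. Nothing in the documents suggests otherwise.
- **The plan's error rate is 0.060.** That holds only if the repeat could rescue a failed first analysis, which the supportive label excludes.
- **Omitting C5b-9 inflates the combined test.** It makes that test conservative. The gain of 1–3% (0.5 SD) or 4–11% (1 SD) in interval width rests on assumed stratum sizes and an assumed baseline correlation.

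**What to change.** 1. **Timing and set.** Either hold the cut-off until the enrolled elevated-stratum patients reach Week 26, or do three things: correct Section 8 to match Section 8.1; add to Section 10 the early cut-off, the exclusion of ongoing patients and the one-dose condition; and give the cut-off set its own name, for example modified ITT. The second route costs only wording. On the first, patients already dosed by 01-Oct-2020 reach Day 183 within 182 days, by 01-Apr-2021 (08-Apr-2021 with the 7-day window), barring an extension of randomised treatment because of COVID-19 (SAP 3.1.8). Patients enrolled later, whom SAP 8.1 mentions without stratum or date, could move this.
2. **Repeat analysis.** Delete the different-endpoints reason. State that only the Week 26 analysis is confirmatory and that the repeat gives no second chance to claim success. No cost.
3. **Combined test.** Add the C5b-9 randomisation stratum to the ANCOVA, at one degree of freedom. The imputation models and van Elteren strata can stay as they are.
4. **Wording.** Use one meaning of secondary population in Sections 3.2.5.3 and 8.
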